### **Outcome Measures**

Activities of Daily Living Scale (ADLS) score (continuous variable), assessed at baseline, 1 hour post-treatment, and 2 weeks of follow-up.

Sport Activity Scale (SAS) score (continuous variable), assessed at baseline, 1 hour post-treatment, and 2 weeks of follow-up.

Oslo Sports Trauma Research Centre (OSTRC) questionnaire score (ordinal variable), assessed at baseline and 2 weeks of follow-up.

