## Outcome Measures

Primary Outcomes:KOS-ADLS: The Activities of Daily Living Scale (ADLS) subscale of the Knee Outcome Survey evaluates symptoms and functional limitations during daily activities. Scores range from 0 to 100, with higher scores indicating better function.

The Sports Activity Scale (SAS) subscale of the Knee Outcome Survey evaluates knee function during sports and higher-level activities. Scores range from 0 to 100, with higher scores indicating better sports-related function.

Secondary outcomes The OSTRC Overuse Injury Questionnaire is a validated self-report tool used to monitor the severity and impact of overuse-related musculoskeletal problems. It assesses the consequences of knee-related problems on sports participation, training volume, performance, and symptom severity. Each question is scored on a graded response scale, and a severity score is calculated, with higher scores indicating greater symptom burden and functional impairment.

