### **Objectives**

The primary objective of this SAP is to define the statistical approach for assessing differences between groups and over time, functional outcomes ADLS and SAS, and overuse injury scores (OSTRC) across the three study groups and time points.

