### **Statistical Methods**

Statistical analysis will be performed using JASP (version 0.95.4.0). A repeated mixed-design ANOVA will be performed with group (Mulligan, Kinesiotaping, Placebo) as the between-

subject factor and time (Baseline, 1 hour, 2 weeks) as the within-subject factor. Interaction effects (group  $\times$  time) will be examined. Post-hoc comparisons will be conducted using a Bonferroni adjustment. Effect sizes will be reported using Cohen's

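### The SAP labels OSTRC ordinal but offers only a mixed ANOVA on means, which could cost the Mulligan-versus-Kinesiotaping comparison much of its power if many players reach the lowest score

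*SAP*

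**What the plan says.** SAP, Outcome Measures: ADLS and SAS are continuous and measured at three visits. The third entry is "Oslo Sports Trauma Research Centre (OSTRC) questionnaire score (ordinal variable", and it is "assessed at baseline and 2 weeks of follow-up".

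SAP, Objectives: the plan covers "overuse injury scores (OSTRC) across the three study groups and time points", so OSTRC is within the planned comparison of arms.

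SAP, Statistical Methods: the only model is introduced with "A repeated mixed-design ANOVA will be performed with group (Mulligan, Kinesiotaping, Placebo) as the between"-subject factor and "time (Baseline, 1 hour, 2 weeks) as the within-subject factor". Post-hoc pairs are Bonferroni-adjusted. No ordinal or rank-based model, assumption check or fallback is given, and no model is assigned to OSTRC by name.

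Protocol, Outcome Measures: OSTRC is the secondary outcome, described thus: "Each question is scored on a graded response scale, and a severity score is calculated". The end of the Protocol's Introduction names it, with the SAS, as a score on which Mulligan is expected to do better.

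**The concern.** The SAP separates OSTRC from the other two scores by scale type and then plans nothing different for it. A mixed ANOVA compares means, treats equal steps on the score as equally important and pools the variance over arms. A severity score has a lowest value. If the better arms reach it, their scores bunch there: the difference in means between them is compressed, and their 2-week spread shrinks while the placebo spread does not.

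Most exposed is Mulligan versus Kinesiotaping, since both arms are active and could both approach the lowest score. A real difference on a hypothesised outcome could then be missed because of the model chosen.

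**Working it through.** **1. The plan's only figure.** Both sample-size sections give partial eta squared 0.816, f = 2.11 and power 1.0. Check: f = sqrt(0.816 / (1 − 0.816)) = sqrt(4.435) = 2.106, and power is 1.000 under every G*Power option tried. The figure reproduces, but it is for ADLS and uses the observed effect. Nothing comparable is given for OSTRC.

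**2. Scale against model.**

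| | ADLS, SAS | OSTRC |
|---|---|---|
| Scale in SAP | continuous | ordinal |
| Visits in SAP | 3 | 2 |
| Time levels in the only model | 3 | 3 |
| Model suited to the stated scale | yes | none named |

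On both scale and visits, the model as written fits ADLS and SAS but not OSTRC. (The Protocol's schedule marks three OSTRC visits. That difference needs reconciling separately.)

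**3. Inputs.** From the documents: N = 60, three arms, Bonferroni. Assumed: 20 per arm, two-sided 0.05, hence 0.05/3 = 0.0167 per pair. Also assumed, because the documents give no OSTRC range, mean, SD or share at the lowest score: a 0–100 score in steps of 5 with a floor at 0, baseline-to-follow-up correlation 0.5, and the means, SDs and reductions below.

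**4. Power for Mulligan versus Kinesiotaping.** With two visits the group-by-time test is the ANOVA on change. Without a floor its power can be checked by formula. The SD of change is SD × sqrt(2(1 − 0.5)) = SD, and the SE of the difference is SD × sqrt(2/20). For SD 20 and a true difference of 20: SE = 6.32, ratio 20/6.32 = 3.16, critical t (57 df) 2.47, power 0.75. That agrees with the simulated 0.75–0.76 in rows 2 and 3. Simulation, 1,000 runs per row:

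| Baseline mean, SD | Reduction (Placebo / Kinesiotaping / Mulligan) | At floor (Kinesiotaping, Mulligan) | ANOVA, no floor | ANOVA, floor | Rank ANCOVA, floor |
|---|---|---|---|---|---|
| 40, 20 | 0 / 15 / 25 | 13%, 27% | 0.20 | 0.14 | 0.24 |
| 40, 20 | 0 / 20 / 40 | 19%, 55% | 0.76 | 0.44 | 0.81 |
| 40, 20 | 0 / 30 / 50 | 35%, 73% | 0.75 | 0.22 | 0.75 |
| 30, 15 | 0 / 25 / 35 | 43%, 69% | 0.36 | 0.09 | 0.37 |
| 50, 15 | 0 / 45 / 60 | 43%, 80% | 0.75 | 0.15 | 0.73 |

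Ordinary ANCOVA gives 0.69 in row 2 and 0.41 in row 3, so baseline adjustment alone recovers part of the loss and ranks add the rest. Against placebo, in the three heavier-floor settings, the mixed ANOVA has 0.96–1.00 and rank ANCOVA 0.997–1.00.

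Two further simulations point the same way:
- About 45% of Kinesiotaping and 75% of Mulligan players at the floor: about 10% for ANOVA on change, 18–21% for ANCOVA, 51% for rank ANCOVA. With a light floor the methods barely differ (6–7%).
- A four-item score (sum 0–12), 49% and 76% at the floor, 500 runs, Monte Carlo error about 2 points: 11% for ANOVA on change, 11% for linear baseline adjustment, 32% for proportional odds. Here linear adjustment alone gained nothing, so how the gain divides depends on the assumed score.

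**5. Error bars.** In the 0–100 simulation (20,000 runs, correlation 0.2–0.8):
- Group-by-time contrasts: the pooled 95% interval covers 93.7%–97.0%, even with up to 80% of an arm at the floor.
- 2-week contrasts with pooled cell variance, between the two improving arms, with 55%–80% of the best arm at the floor: the SE is 1.23–1.59 times its true value and coverage is 98.5%–99.8%, so the interval is too wide.
- The same 2-week contrasts against placebo: coverage 94.7%–97.9%.
- With no arm difference, type I error is 0.048–0.051.

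**The case against.** **No analysis is assigned to OSTRC.** The three time levels match only ADLS and SAS in the SAP, so one can argue that OSTRC was left without a model rather than given a wrong one. The effect-size sentence in Statistical Methods also breaks off, so text may have been lost. This stands as a caution. On either reading the secondary outcome has no model that fits its stated scale, and the remedy is the same.

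**A reader might infer that the Protocol and SAP contradict each other.** They do not. A score calculated from graded items can be treated as ordinal. The conflict lies within the SAP, between Outcome Measures and Statistical Methods.

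**A reader might infer that the ANOVA gives wrong error bars and too many false positives.** With assumed 2-week SDs of 0.5 : 1 : 1.5 (Mulligan : Kinesiotaping : Placebo), the pooled variance is (0.25 + 1 + 2.25)/3 = 1.167. The Kinesiotaping–Placebo SE is then sqrt(2.333/3.25) = 0.85 of its true value, and the size is 4.3%–4.4%. That exceeds only the 1.67% per-pair level. If that pair is the only true null, the same figure is the family-wise error and stays below 5%. With Kinesiotaping and Placebo identical, size is 3.8% when Mulligan's SD is half theirs and 5.2% when it is zero, so family-wise control essentially holds. The SD pattern is also awkward: if the floor is what narrows Kinesiotaping's spread, that arm has improved and is not null against placebo. The SAP does not say that its post-hoc tests use this error term.

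**The floor is assumed.** This stands. It is plausible, because eligibility requires active players and sets no minimum OSTRC score, but the documents neither show it nor rule it out.

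**Conclusion.** The point holds in limited form. The firm finding is the mismatch between the SAP's ordinal label for OSTRC and its only model, and it needs no assumption about the data.

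The cost is conditional. With about 75% and 45% of the Mulligan and Kinesiotaping arms at the lowest score, power for that pair is roughly 10% for ANOVA on change against 20% for linear baseline adjustment and 50% for rank ANCOVA. With a light floor the loss is small (0.20 to 0.14 in the first row of the table), and under a heavy floor little is lost against placebo. Pooled 2-week contrasts between the improving arms can then be too wide, which is conservative. All of these sizes rest on assumed OSTRC distributions and 20 players per arm. The plan should be changed on this point, but nothing here shows the planned group-by-time test to be invalid.

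**What to change.** In SAP Statistical Methods, limit the mixed ANOVA to ADLS and SAS. For OSTRC:

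- State how the severity score is built and its range, and keep the ordinal label.
- Compare arms on the 2-week score, adjusted for baseline OSTRC, with a proportional-odds model. Name rank ANCOVA as the alternative if categories are too sparse or proportional odds is implausible, and set the rule for switching before arms are compared.
- Report all three pairwise comparisons with confidence intervals at the same Bonferroni level.
- Give the mean difference with unequal-variance standard errors as a supplement.

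Baseline and 2 weeks are the OSTRC visits on which both documents agree, so no new data are needed. The cost is a few sentences and one extra model. The small downside is that an odds ratio or rank-based effect is less familiar than a difference in points, which the supplementary mean difference offsets. Since the SAP already reports an observed ADLS effect, the amendment should be dated and say which results were known when it was made.

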### **Study Design**

This study was designed as a parallel group randomized controlled clinical trial with three intervention arms: Mulligan Mobilization with movement MWM, Kinesiotaping, and Placebo with repeated measurements at baseline, 1 hour, and 2 weeks after treatment.

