## Timeline / Schedule of Assessments

Outcome /Assessment	Baseline treatment	pre	1 hour post treatment	2 weeks post treatment
KOS-ADLS ; ADLS	*		*	*
SAS	*		*	*
OSTRC	*		*	*`

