### **Study Design**

The present study will be designed as a parallel group randomized controlled clinical trial with three intervention arms: Mulligan mobilization MWM, kinesiotaping, and placebo, with repeated measurements at baseline, 1 hour, and 2 weeks of follow-up. The study will be conducted over a two- week intervention period as a part of a doctoral research project. The study will be carried out with CONSORT reporting guidelines (Schulz, K.F. et al., 2010)

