### **Handling Missing Data**

No missing data are expected. All collected data will be included in the final analysis. No imputation methods will be applied.

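### OSTRC has three visits in the Protocol schedule but two in the SAP, and the SAP's only model, with three time levels, cannot be fitted to the two-visit score

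*SAP*

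**What the plan says.** **Visits.** In the Protocol's Timeline / Schedule of Assessments, the OSTRC row is marked in every column, including "1 hour post treatment", exactly as for ADLS and SAS. The Protocol's Study Design describes the trial "with repeated measurements at baseline, 1 hour, and 2 weeks after treatment", and the SAP's Study Design does so "with repeated measurements at baseline, 1 hour, and 2 weeks of follow-up". Neither makes an exception for OSTRC. The SAP's Outcome Measures section does: "Oslo Sports Trauma Research Centre (OSTRC) questionnaire score (ordinal variable), assessed at baseline and 2 weeks of follow-up". The two entries directly above it, for ADLS and SAS, both include the 1-hour visit.

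**Model.** SAP Statistical Methods gives one model, a mixed ANOVA with group between subjects and "time (Baseline, 1 hour, 2 weeks) as the within-subject factor". It does not name the outcomes it covers, gives no separate OSTRC analysis, and mentions no check of or correction for sphericity. SAP Objectives includes "overuse injury scores (OSTRC) across the three study groups and time points" in what the plan must analyse.

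**Missing data.** SAP Handling Missing Data states: "No imputation methods will be applied". The same section commits to using everything that is collected in the final analysis.

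**The concern.** OSTRC carries the whole secondary objective and one side of the third, which relates the fall in OSTRC to gains in ADLS and SAS. It is also named in the study hypothesis. Its analysis depends on which visits exist, and the documents give two answers.

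On the SAP's answer, the only model asks for a time level that has no data and may not be imputed. On the Protocol's answer, the model can be fitted, but the 1-hour score may track baseline closely. The differences between visits would then have unequal variances, and an uncorrected repeated-measures F test can reject too often.

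If the conflict stays open, the choice between a two-visit and a three-visit analysis can be made after the data are seen. The sample size sections of both documents already report an observed ADLS interaction, so it matters to record when that choice is made.

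**Working it through.** **1. The plan's own figure.** The only effect size and power stated are for ADLS: partial eta squared 0.816, f = 2.11, power 1.0, N = 60.
- f = √(0.816 / 0.184) = 2.106, which rounds to 2.11.
- With noncentrality f² × N = 4.435 × 60 = 266 on (4, 114) degrees of freedom, power is 1.000.

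The figure reproduces. It concerns ADLS only and says nothing about OSTRC.

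**2. The passages side by side.**

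| Source | OSTRC time points |
|---|---|
| Protocol, Schedule of Assessments | 3 |
| Protocol, Study Design | 3 (no exception) |
| SAP, Study Design | 3 (no exception) |
| SAP, Outcome Measures | 2 |
| SAP, Statistical Methods (time factor) | 3 |

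Two visits cannot fill three levels, and the SAP does not allow the third to be imputed.

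**3. Upper end of the inflation.** Assume alpha 0.05 and 20 per arm; neither is stated. With m time levels, the group-by-time test has 2(m − 1) and 57(m − 1) degrees of freedom: (4, 114) for m = 3 and (2, 57) for m = 2.

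Suppose the 1-hour score equals baseline exactly. Every within-person contrast is then a multiple of the single change from baseline to 2 weeks, so the ratio of interaction to error sums of squares is the same in both analyses. The F statistics coincide too, because 114/4 = 57/2 = 28.5. Only the critical value differs: 2.451 on (4, 114) against 3.159 on (2, 57). The true type I error of the uncorrected three-level test is therefore P(F(2, 57) > 2.451) = 0.095. With five-category scores in place of normal ones, simulation gives 0.097.

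**4. Between the extremes.** Each row is 20,000 simulated trials with no true effect and both correlations with week 2 set at 0.5. Simulation error is about √(0.05 × 0.95 / 20,000) = 0.0015, or roughly 0.2 percentage points.

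| Baseline to 1-hour correlation | Uncorrected | Greenhouse-Geisser |
|---|---|---|
| 0.5 | 5.2% | 4.9% |
| 0.7 | 5.6% | 4.8% |
| 0.8 | 6.5% | 5.1% |
| 0.9 | 7.9% | 5.2% |
| 0.95 | 8.5% | 5.0% |
| 0.99 | 9.5% | 5.2% |

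The correlation with week 2 matters less. At a baseline to 1-hour correlation of 0.9, the uncorrected rate is 8.1% if the week-2 correlations are 0.3 and 6.7% if they are 0.7.

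**5. Two visits only.** A two-level mixed ANOVA on (2, 57) degrees of freedom rejects 5.1% of the time with normal scores and 4.9% with five-category scores.

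**6. Which two-visit analysis.** The two-level interaction test is a comparison of change scores. With equal variances scaled to 1 and baseline to 2-week correlation r, the error variance is 2(1 − r) for change scores and 1 − r² for the 2-week score adjusted for baseline.
- r = 0.5: 1.00 against 0.75.
- r = 0.7: 0.60 against 0.51.

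Baseline adjustment is more precise in both cases.

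**The case against.** **The model may not be meant for OSTRC as written.** Statistical Methods names no outcome, and a two-level version of the same ANOVA is an obvious adaptation that holds 5%. This stands as a limit on the point: OSTRC is not impossible to analyse. But SAP Objectives puts OSTRC in scope and no other model is given, so the adaptation is left to the analyst.

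**Inflation is not inevitable.** A reader might infer that OSTRC either cannot be analysed or must be tested at an inflated error rate. The documents do not support that. A rate near 9.5% needs a 1-hour score that almost duplicates baseline, and no correlation is reported. At 0.5 to 0.7 the rate is close to nominal, and a standard sphericity correction removes the excess in every setting tried.

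**A 1-hour OSTRC score need not be empty of information.** It is tempting to say that participation, training volume and performance cannot change within an hour of a 5-minute session. The Protocol's description goes further: "It assesses the consequences of knee-related problems on sports participation, training volume, performance, and symptom severity". Symptoms could change in that time, and no recall period is stated. A high correlation with baseline is plausible, but it remains an assumption.

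**The SAP's two visits are not self-evidently the right ones.** Three other sections imply three, and dropping the 1-hour score would remove the third objective's OSTRC relationship at that visit. This stands, and the sponsor has to decide. Setting aside scores already collected would also conflict with the SAP's commitment to include all collected data.

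**Conclusion.** The contradiction over OSTRC visits is explicit, and the SAP's only model cannot be fitted to OSTRC as the SAP defines it. That conclusion needs no simulation. It rests on reading the single model as covering OSTRC, which SAP Objectives and the absence of any alternative support.

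The error-rate consequence is conditional. It applies only if a 1-hour score enters the three-level test uncorrected. The rate then runs from about 5% (correlation 0.5 to 0.7), through 7 to 8% (0.9), to about 9.5 to 10% when the 1-hour score nearly copies baseline. Alpha 0.05, 20 per arm and all correlations are assumptions.

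This should be fixed. It falls short of the most serious grade because the outcome is secondary and the ADLS and SAS analyses are unaffected.

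**What to change.** 1. Reconcile the Protocol schedule with SAP Outcome Measures on the OSTRC visits, and align both Study Design sections. Record when the decision was made and whether 1-hour scores already exist.
2. State in SAP Statistical Methods that the three-level time model applies to ADLS and SAS.
3. Specify the main OSTRC analysis as a between-arm comparison of the 2-week score adjusted for the baseline score. As the SAP labels the score ordinal, use an ordinal model such as proportional odds, or justify treating the severity score as numeric. This analysis works under either schedule.
4. If 1-hour OSTRC scores exist, report them descriptively or in a three-level model with a Greenhouse-Geisser correction. Either way, the commitment to include all collected data is kept.

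The cost is one reconciled schedule entry and a few SAP sentences. No extra participants or visits are needed.

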### **Statistical Methods**

Statistical analysis will be performed using JASP (version 0.95.4.0). A repeated mixed-design ANOVA will be performed with group (Mulligan, Kinesiotaping, Placebo) as the between-

subject factor and time (Baseline, 1 hour, 2 weeks) as the within-subject factor. Interaction effects (group  $\times$  time) will be examined. Post-hoc comparisons will be conducted using a Bonferroni adjustment. Effect sizes will be reported using Cohen's

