the injury rate in young athletes, on the one hand, and the assessment of the level of activity and sports functionality, on the other. Although a good part of the research is focused on rehabilitation through conservative management of sports injury in young basketball players (Sos-Tirado, M. et al., 2024). This randomized study aimed to evaluate the effect of the Mulligan MWM technique, the Kinesiotaping technique, and a placebo intervention in young U16-U20 basketball players on reducing symptoms of knee injuries and improving functionality and sports levels. This study hypothesized that the Mulligan group would have a more significant improvement in the KOS-SAS and OSRTC scores.

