### **Sample Size**

The sample size was calculated using G \*power- 3.1 software (Faul, F. et al., 2007) while we used the actual sample size (N=60) and conducted post-hoc power analysis for the primary outcome, ADLS, and mixed ANOVA. Interaction was  $\eta^2p = 0.816$  (Cohen's  $f = 2.11$ ), and the statistical power indicated a very high (1.0).

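### The SAP analyses ADLS and SAS by a group-by-time ANOVA with baseline as an outcome and undefined post-hoc tests, so no stated contrast answers the primary objective and precision is lost

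*SAP*

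**What the plan says.** The SAP's Statistical Methods section plans a mixed ANOVA with group (three arms) between subjects and "time (Baseline, 1 hour, 2 weeks) as the within-subject factor". The group-by-time interaction is to be examined, and then "Post-hoc comparisons will be conducted using a Bonferroni adjustment". It does not say which pairs are compared, at which times, on which scale (score or change), or how many tests share the adjustment. No baseline-adjusted model is mentioned, and the section is silent on sphericity.

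The protocol's primary objective is a three-arm comparison of function and sports activity, with no contrast or time point singled out. The Introduction is directional: "This study hypothesized that the Mulligan group would have a more significant improvement in the KOS-SAS and OSRTC scores". It names no time point either. The protocol lists ADLS and SAS together under primary outcomes, while the SAP's Sample Size section calls ADLS the primary outcome. The schedule of assessments has both scales collected at baseline, 1 hour and 2 weeks.

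**The concern.** The question is whether one arm does better than another. A 3 × 3 interaction test asks something broader: whether the three arms' profiles over the three times depart from parallel in any way. A short-lived difference at 1 hour, or a difference between Kinesiotaping and the other two arms, can make it significant. The answer therefore rests on the follow-up comparisons, and those are left open.

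Three things are at stake:

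- **Interpretation.** A significant interaction may be read as the answer to the primary objective when it is not.
- **Analyst choice.** The size of the Bonferroni family decides how strict each comparison is. Both documents already quote an observed ADLS interaction, so that choice can now be made with results in view.
- **Precision.** Baseline scores are collected anyway. Using them as an outcome level instead of a covariate discards information.

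**Working it through.** **Inputs from the documents.** N = 60 in total (Sample Size, both documents); three parallel arms; three times; no missing data expected; partial eta squared 0.816 and f = 2.11 for the ADLS interaction, with stated power 1.0.

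**Assumptions, because the documents give no figure.** 20 per arm; two-sided alpha 0.05; SD = 1 at each time, so effects are in SD units; baseline-to-follow-up correlation rho of 0.3, 0.5 or 0.7; true difference 0.5 or 0.8 SD.

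**1. The plan's own figure.** f = √(0.816 / 0.184) = 2.106, which rounds to 2.11. With df = (3 − 1)(3 − 1) = 4 and (60 − 3)(3 − 1) = 114, power is 1.000 under every noncentrality convention tried. The figure reproduces. It is the power of the 4-df interaction at the effect already observed, so it says nothing about any single between-arm contrast.

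**2. What the interaction responds to.** Suppose one arm differs by d at 1 hour only. The squared interaction effects then sum to (2/3)(2/3)d² = 4d²/9. With equal correlations, the noncentrality is λ = 20 × (4d²/9) / (1 − rho). For d = 0.8 and rho = 0.5, λ = 20 × 0.2844 / 0.5 = 11.4, and the power is 0.76. A Kinesiotaping-only difference of 0.8 SD at both follow-up times gives the same sum and the same 0.76, with Mulligan and placebo identical throughout.

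With unequal correlations (baseline to 1 hour 0.9, the other two 0.5), simulation of a 0.5 SD effect at 1 hour only gives rejection about 44% of the time uncorrected and 33% with Greenhouse-Geisser.

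**3. Precision.** The residual variance is 1 − rho² for ANCOVA and 2(1 − rho) for change from baseline. The ratio is (1 − rho²) / [2(1 − rho)] = (1 + rho)/2. Power for one 0.8 SD contrast uses the noncentral t with ncp = 0.8 / (SD × √(2/20)), on 56 df for ANCOVA and 57 df otherwise:

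| rho | Variance ratio | ANCOVA ncp | ANCOVA power | Change ncp | Change power |
|---|---|---|---|---|---|
| 0.3 | 0.65 | 2.65 | 0.74 | 2.14 | 0.56 |
| 0.5 | 0.75 | 2.92 | 0.82 | 2.53 | 0.70 |
| 0.7 | 0.85 | 3.54 | 0.94 | 3.27 | 0.89 |

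If the post-hoc tests compare follow-up scores without using baseline, the power is 0.70 at every rho, again below ANCOVA.

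**4. The undefined Bonferroni family.** Take a 0.8 SD difference in follow-up scores (ncp = 0.8 / √(2/20) = 2.53, 57 df):

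- 3 pairs at one time, alpha 0.05/3 = 0.0167: power 53%.
- 9 pairs (3 pairs × 3 times), alpha 0.05/9 = 0.0056: power 37%.
- All pairs of the 9 cells, 9 × 8 / 2 = 36, alpha 0.05/36 = 0.00139: power 22%.

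Three baseline-adjusted contrasts at alpha 0.0167 have power 67% at rho = 0.5.

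**5. Sphericity.** Simulated type I error of the interaction test, if no correction is applied (correlations in the order baseline to 1 hour, baseline to 2 weeks, 1 hour to 2 weeks):

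- Equal correlations: about 5%.
- 0.8/0.7/0.7: about 5.2%.
- 0.7/0.5/0.5: about 5.6%.
- 0.9/0.5/0.5: about 7.6% (about 5% with Greenhouse-Geisser).
- 0.95/0.5/0.5: about 8 to 9%.

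**The case against.** Much can be said for the plan, and part of it stands.

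- **A reader might infer that the omnibus ANOVA is the only analysis.** It is not. Bonferroni comparisons are planned and could include Mulligan against each comparator at either follow-up. They are undefined, not absent.
- **A reader might take 2 weeks as the target and a 1-hour effect as noise.** The documents do not support that. They list 1 hour and 2 weeks side by side for ADLS and SAS, so a 1-hour effect is a legitimate finding. What is missing is any statement of which time is primary.
- **A reader might conclude that type I error exceeds 5%.** That needs both unequal correlations and no correction. The SAP does not say the test is uncorrected, and the available text of Statistical Methods breaks off in its sentence on effect sizes. Inflation is plausible, because 1 hour and 2 weeks are very unequal gaps, but it is not established.
- **The omnibus test is not always the weaker one.** At rho = 0.7, with Mulligan 0.8 SD better than both other arms, it has power 0.945 against 0.936 for a single ANCOVA contrast. The two test different hypotheses, so the fair comparison is ANCOVA with the change score; there ANCOVA has the smaller variance at every rho below 1.
- **The choice is largely one of efficiency.** With randomisation and complete data, the planned group-by-time contrasts are unbiased. This stands, and it limits the severity.

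**Conclusion.** The point holds in a limited form. Baseline is an outcome level, no covariate adjustment is mentioned, and no primary contrast, time point or comparison family is stated. A significant interaction therefore does not identify a Mulligan benefit.

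The size depends on assumptions the documents cannot settle (20 per arm, two-sided 0.05, the correlations and the true difference). Over rho from 0.3 to 0.7, like-for-like power for a 0.8 SD contrast rises by 0.18, 0.12 or 0.05 when baseline becomes a covariate, so the gain shrinks as the correlation grows. The open Bonferroni family matters more: it moves power between 53% and 22%.

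The stated power of 1.0 does not answer this, since it refers to the omnibus test at its observed effect. The plan should be changed, but the planned analysis is imprecise and under-specified, not invalid.

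**What to change.** - **Primary model.** Analyse ADLS and SAS by ANCOVA of the follow-up score on arm and baseline score.
- **Primary time point.** Name one. Two weeks is a recommendation, as the end of the two-week intervention period described in the SAP; the documents name none. State what the 2 weeks are counted from, because the protocol's schedule labels that visit as post treatment. Make 1 hour secondary with the same model.
- **Contrasts.** Limit the family to Mulligan versus placebo, Mulligan versus Kinesiotaping and Kinesiotaping versus placebo. Use Holm, which is never less powerful than Bonferroni. State alpha and how it is shared between ADLS and SAS. Report each contrast with a 95% confidence interval in points on the 0 to 100 scale.
- **Supportive analysis.** Keep the mixed ANOVA, with Greenhouse-Geisser correction.
- **Transparency.** Because both documents already report an observed ADLS interaction, date the change, label it post hoc, and report the analysis as now planned alongside it.

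The cost is one SAP paragraph, a short re-run on scores the schedule already collects, and the post hoc label, which weakens the confirmatory standing of the new analysis.

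OSTRC is outside this fix. The SAP calls it ordinal and measures it at two times, while the protocol's schedule adds 1 hour. Those passages must be reconciled and OSTRC given its own analysis.

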### **Objectives**

The primary objective is to compare the effect of Mulligan, Kinesiotaping and Placebo in improving the functionality and scale of sports activity in U16-U20 basketball players.

The secondary objective is to evaluate the effect of the Mulligan, Kinesiotaping, and Placebo intervention in decreasing the level of overuse injuries in U16-U20 basketball players.

The third objective is whether each of the techniques, Mulligan, Kinesiotaping, and Placebo, has an impact on the relationship between decreasing the rate of OSTRC overuse injury and increasing the ADLS functional scale and SAS sports activity scale in U16-U20 basketball players.

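### Bonferroni is a valid adjustment for the post-hoc arm comparisons, but Holm gives the same 5% familywise guarantee and never less power; the gain on Mulligan versus Kinesiotaping is 0 to about 18 points, depending on inputs the plan does not state

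*SAP*

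**What the plan says.** The SAP (Study Design) describes a "parallel group randomized controlled clinical trial with three intervention arms". Its Statistical Methods section specifies a mixed ANOVA with arm as the between-subject factor and "time (Baseline, 1 hour, 2 weeks) as the within-subject factor", examines the interaction of the two, and adds: "Post-hoc comparisons will be conducted using a Bonferroni adjustment". It does not say which comparisons form the family, at which visit they are made, or at what significance level.

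The pairwise comparisons matter because the Protocol (Objectives) states: "The primary objective is to compare the effect of Mulligan, Kinesiotaping and Placebo in improving the functionality". The Protocol (Introduction) expects Mulligan to come out ahead: "This study hypothesized that the Mulligan group would have a more significant improvement in the KOS-SAS and OSRTC scores".

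On size and power, the SAP (Sample Size) reports a total of 60 and says of the ADLS interaction that "the statistical power indicated a very high (1.0"). That is observed power for the overall interaction. Neither document gives an effect size, an SD or a power target for any single pair of arms.

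**The concern.** Bonferroni tests each of three pairs at 0.05/3 = 0.0167, whatever the other two pairs show. Holm orders the three p-values and compares the smallest with 0.05/3, the next with 0.05/2 and the last with 0.05, stopping at the first failure. Each Holm threshold is at least as large as Bonferroni's, so Holm cannot lose a rejection that Bonferroni makes. Both hold the familywise error at or below 5% whichever null hypotheses are true.

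The extra rejections matter most for Mulligan versus Kinesiotaping. If both active arms beat placebo, this is likely to be the smallest difference and so the last in Holm's order, where the threshold is 0.05 rather than 0.0167. With about 20 players per arm, a real moderate advantage over the active comparator could be reported as not significant only because the single-step version was chosen.

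**Working it through.** **The plan's own figure.** From the partial eta squared of 0.816, f = √(0.816/0.184) = 2.106, which rounds to the stated 2.11. With noncentral F on 4 and 114 df, α = 0.05 and λ = f² × 60 = 266, power is 1.000. The stated figure reproduces, but it concerns the overall interaction and says nothing about one pair.

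**Inputs.** From the documents: N = 60, three arms, Bonferroni. Assumed because not stated: 20 per arm, two-sided α = 0.05, a family of three pairs for one outcome at one time point, normal data with common SD (pooled df = 60 − 3 = 57), and a standardised Mulligan-Kinesiotaping difference *d* varied over a range.

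**Largest possible gain.** If placebo is so far below both active arms that its two comparisons are always rejected, Holm tests the remaining pair at 0.05. Power comes from the noncentral t with noncentrality d × √(20/2) = 3.162d. The critical values are 2.467 (α/3) and 2.002 (α).

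| d | Bonferroni % | Holm, placebo far below % | Gain (points) |
|---|---|---|---|
| 0.2 | 3.9 | 9.5 | 5.6 |
| 0.5 | 19.7 | 34.3 | 14.6 |
| 0.7 | 40.7 | 58.6 | 17.9 |
| 0.8 | 52.9 | 70.1 | 17.2 |
| 1.0 | 75.4 | 87.5 | 12.0 |
| 1.2 | 90.4 | 96.2 | 5.8 |
| 1.5 | 98.7 | 99.7 | 0.9 |

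Gains are taken before rounding. The peak on the grid is 17.9 points, at d = 0.7.

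**Placebo below both arms, at a finite distance** (simulation; arm means in SD, Mulligan/Kinesiotaping/placebo):

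| Means | Bonferroni % | Holm % | Gain (points) |
|---|---|---|---|
| 1.2/0.5/0 | 40.6 | 49.1 | 8.5 |
| 1.0/0.3/0 | 40.7 | 46.7 | 6.0 |
| 1.6/0.8/0 | 53.0 | 66.5 | 13.5 |

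**Kinesiotaping equal to placebo.** The pair seldom reaches Holm's 0.05 step, so the gain is small: 0.3 points at d = 0.2, 1.5 at 0.5, 3.3 at 0.8 and at 1.0, 2.0 at 1.2, and 0.5 at 1.5.

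**Familywise error** (simulation). With all arms equal it is 4.3% for both methods. With one true null pair it is about 1.7% for Bonferroni. For Holm it rises with the distance of the third arm, to roughly 3.6% at 1 SD and 5.0% at 2 SD. In no simulated trial did Bonferroni reject a pair that Holm missed.

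**Family size.** Three arms by three visits make 9 cells and 9 × 8/2 = 36 cell pairs. If Bonferroni covered all 36, power at d = 0.7 would be 14.0%, against 40.7% for three pairs.

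**The case against.** Bonferroni is standard and valid, and no contradiction or error has been shown. That stands.

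The gain depends on inputs that the documents do not supply: allocation, significance level, family and the size of the Mulligan-Kinesiotaping difference. That also stands. A reader might infer that the trial gives up 6 to 18 points of power. The documents do not support this as a fact about the trial. The very large observed ADLS interaction does not fix the gap for this pair, and if that gap is 1.5 SD or more the loss is under 1 point.

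A reader might also go further in three ways:

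- **That Bonferroni buys nothing.** It shares the nominal 5% bound with Holm, but it is stricter when only some nulls are true (about 1.7%) and comes with simple simultaneous confidence intervals.
- **That a three-arm test at 5% followed by unadjusted pairs is better still.** Its average power is higher in these scenarios, but it does not strictly dominate. At Bonferroni's cutoff t = 2.467 the three-arm F can be as low as 3.04, below its critical value of 3.16. Bonferroni rejected a pair that this procedure missed in up to about 0.4% of simulated trials. Written as a 2-week test, it would also drop the 1-hour visit and replace the group-by-time analysis.
- **That the plan pays for multiplicity twice.** The SAP does not make the post-hoc comparisons conditional on a significant overall test.

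Finally, both Sample Size sections report an observed ADLS effect, so results appear to have been seen. Moving to a more liberal rule now could look driven by the data. This does not remove the case for Holm, but it governs how the change must be documented.

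**Conclusion.** The point holds as an efficiency improvement. That Holm is never less powerful than Bonferroni at the same strong 5% familywise error is a mathematical fact and needs no assumption about effects. The size does need assumptions. For 20 per arm, two-sided 5% and three pairs for one outcome at one time point, the gain on Mulligan versus Kinesiotaping lies between 0 and about 18 points. It is worthwhile when the difference is moderate and placebo is clearly below both arms, and negligible when the difference is very large.

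The undefined family limits how far these figures carry over. At d = 0.7, a family of 36 instead of three would cost 40.7 − 14.0 = 26.7 points, more than the choice between Holm and Bonferroni. Any power recovered by settling on three pairs should not be credited to Holm.

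**What to change.** In the SAP (Statistical Methods), replace the Bonferroni sentence with, for example: *Pairwise comparisons between the three arms will be Holm-adjusted within each outcome and time point (family of three, two-sided 5%).* Leave the mixed ANOVA and the visits unchanged. Holm works on p-values, so it applies whichever test is used for the ordinal OSTRC score.

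The change needs no new data or players. Its costs are:

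- **Intervals.** Holm has no simple matching simultaneous confidence intervals. Bonferroni intervals can still be reported, with a note that one may include zero where Holm rejects.
- **Error under partial nulls.** This rises from about 1.7% towards 5%, within the stated bound.
- **Scope.** The 5% applies within each outcome and time point. It does not cover ADLS, SAS and OSTRC together, or the visits together.
- **Timing.** Date the amendment, state what results were known at that date, and report the Bonferroni-adjusted result beside the Holm result.
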